factors leading to this complex disease are thought to be the cause that can result in lesions

(small areas of damage) in the brain and spinal cord, the central nervous system (CNS). These

lesions are thought to be the cause of relapses and disability in MS.

Condition: Multiple Sclerosis, Relapsing-Remitting

Intervention

Drug: A (oral cocktail formula of structured lipids),

Drug: B (PLP10) (oral cocktail formula of structured molecules, lipids and vitamins),

Drug: C (antioxidant vitamin),

Drug: Placebo (virgin olive oil)

Phase: II (Proof-of-Concept)

Investigator/Trial Location: By PALUPA Medical Ltd. At The Cyprus Institute of Neurology and

Genetics

Study Type: Interventional

Study Design: Allocation: Randomized

Endpoint Classification: Efficacy /Safety Study

Intervention Model: Parallel Assignment

Masking: Double Blind (Subject, Investigator, Total involved Personnel,

Outcomes Assessor)

Primary Purpose: Treatment/adjuvant treatment

Investigator Specialties: Neurology, Clinical Biochemistry (Lipidology, Immunology) and Clinical

Dietitian. All investigators are experienced and with more than 20 years in practice.

Enrollment: Total number of MS patients in Cyprus meeting the required criteria.

Arms	Assigned Interventions
Group 1: Experimental	Drug: A†
A, Oral Intervention: Drug: A (structured lipids)	Cocktail of EPA/DHA re-esterified triglycerides, triglycerides of LA/GLA, vitamins A, E as alpha tocopherol, 15.3 ml, oral, daily 30 minutes before dinner, for 30 months.
Group 2: Experimental	Drug: PLP10†
B-PLP10, Oral Intervention: Drug: B-PLP10 (structured lipids and vitamins)	Cocktail of EPA/DHA re-esterified triglycerides, triglycerides of LA/GLA, vitamins A, E as alpha tocopherol, E as gamma tocopherol, 16.0 ml, oral, daily 30 minutes before dinner, for 30 months.
Group 3: Experimental	Drug: C†
C, Oral Intervention: Drug: C (antioxidant vitamin)	Gamma tocopherol (vitamin E isoform/antioxidant), 760 mg (in pure virgin olive oil as a vehicle), 17.0 ml oral, daily 30 minutes before dinner, for 30 months.
Group 4: Placebo Comparator	Drug: Placebo†
D-Placebo Oral Intervention: Drug: Placebo	Placebo (Pure Virgin Olive Oil), 17.0 ml, oral, daily 30 minutes before dinner, for 30 months.

Preparations for the daily intervention formula agent dosages will be:

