This is an ITT study with a proof-of-concept purpose. The main question that has to be answered is primarily the ability of the interventions to reduce the annual relapses rate and secondly the disability accumulation when used in RRMS patients and how safe it is vs. placebo. All patients who prematurely discontinue the study drug will be encouraged to continue in the study and follow-up until the end of the planned treatment period, regardless of the treatments received. The data collected will be included for ITT analyses. The main analysis of ARR will include all confirmed (associated with new or worsening of pre-existing neurological signs, increase of at list 0.5 score on EDSS) relapses during the study, including relapses reported after study drug discontinuation. The lost to follow missing data will be handled by an appropriate statistical

method and included in the intention to treat analysis (ITT). The overall key analysis should be based on per-protocol (excluding all protocol violations) supported by the ITT analyses.

Other:

An independent Data Monitoring Committee (DMC) will monitor and review all clinical trial data on a regular basis (by the funder).

Investigators adherence will be also monitored by DMC through CRF follow up.

Duration of Study per Patient

The clinical study period is approximately 43 months total, including a screening period up to 1 month, a 6 month normalization, 24 months treatment period and 12 months extended follow up period, after completion. The actual research period is for a total of 30 months including 6 months normalization and 24 months treatment periods.

Methods

The whole procedure follows the clinical trial guidelines as required by the USA Food and Drug Administration (FDA), European Medicines Agency (EMA) and according to the standards of the International Conference of Harmonization (ICH). The Clinical study is in agreement with the rules of Good Clinical Practice (GCP).

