CING is a tertiary accredited neurological center. All patients should give a written informed consent before enrolment. The study protocol is developed by the investigators and should be approved by the National ethics committee. Patient consent forms (CFs) and case report forms (CRF) documents are set up by the investigators according to the international guidelines and the needs of the trial protocol/ design and approved by the independent committee assigned by the funder. Study data (CRFs will be completed as required per patient per assessment) will be collected by the involved neurologist and forwarded to be held and blindly analyzed centrally according to the guidelines set-up by the Helix Incubator Organization of Nicosia University (HIONU) as an independent organization assigned by the funder. A CRF copy should be kept by

the clinical site. During the study, investigators and safety/ monitoring committee representatives should meet once a year to discuss study progress.

Randomization and Masking

Patients will be randomly assigned to the four intervention groups. Randomization will be centralized and the randomization scheme will be generated, performed and securely stored by HIONU.

Sample size as a result of the absence of any previous reported data and due to the novelty of the intervention will strictly be based on the total eligible to participate relapsing remitting MS patients in Cyprus.

Responsibilities will include, but not limited to regulatory management, clinical trial management, quality control (use only of accredited laboratories) and administrative activities. External committees (ie. independent safety/ monitoring committee etc.) will be set up by the funder. Randomization scheme will be securely stored by HIONU, with the investigators, patients, all study personnel, medical monitors, clinical research associates, statisticians/bioanalysts, neuroradiologist and pharmacist being unaware of treatment assignments throughout the study.

If knowledge of the study drug will be needed to manage a patient's condition, such as in the occurrence of a serious adverse event, the patient will not be given further treatment with the study drug and should continue to be medically followed.

Study Procedures and End Points

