The key secondary endpoint is the **time to confirmed disability progression** defined as an increase of 1.0 on the EDSS from a baseline score, confirmed after 6 months, with an absence of an ongoing relapse at the time of assessment (progression cannot be confirmed during a relapse) and with no documented relapse during the 6-months period needed for the confirmation. The final EDSS score will also be confirmed 6 months after the end of the study.

Relapses should be treated with methylprednisolone at a dose of 1g intravenously per day, for three consecutive days followed by prednisolone by mouth at a dose of 1mg/kg of weight per day on a tapering scheme for three weeks.

Hematological (full blood count) and Biochemical analyses should be performed at enrolment, baseline, 12 months and 24months and at the end of the extended period; performed at accredited laboratory.

Blood should be collected from all randomized patients at the time of enrolment and at every scheduled clinical assessment and during relapses. Blood tubes should be appropriately labelled including date, patients' code, number of scheduled assessment, for every blood handling step. A portion of 2 ml total blood volume per patient (in anticoagulant solution) should be drawn and stored refrigerated (4°C) for the lipid extraction procedure (from red blood cells) within 24 hrs according to standard protocol.

Sample Size Estimation

Power calculations could not be done before the study because of the lack of information from previous studies on potential effect sizes. Based on the population size of our country and the centre of reference (CING) we believe that we will probably be able to enroll enough patients for this proof-of-concept study. The scientific knowledge/background of the agents used, novelty of the assessed interventions and the study-protocol design/set-up will be contributing to valuable information. Hopefully the "eligible" final enrolled sample size will be enough to collect quality data able to answer the addressed proof-of-concept questioned - efficacy indication. There is no any matter of ethical conflicts since all interventions will be used as adjuvant. Sample size will strictly be based on this subjects' availability parameter.

Brief Statistical Methods

The study will be considered successful if there is a significant difference between the treatments for either of the two endpoints.

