Baseline characteristics will be compared across all intervention groups by ANOVA or Kruskal-Wallis rank test for continuous variables and by an exact chi-squared test for categorical variables, as appropriate.

Each test will be performed with a significance level of 0.05 (P-values will be two-tailed).

Primary Endpoint

Annualized Relapse Rate (ARR):

A Poisson regression/ negative Binomial analysis will be used to analyze this endpoint. The analysis will allow for likely overdispersion due to within-subject correlations by basing standard errors on the empirical estimator of the parameter covariance matrix. The fixed factors in the model will include treatment and relevant pre-specified covariates.

The relapse rate will be calculated as the total number of relapses divided by the total number of patient-years followed for each treatment group. ARR differences will also be calculated among all comparable parameters and reported as percent difference (relative reduction).

Secondary Endpoint

Time to Confirmed Disability Progression:

For the secondary end-point outcome, the time to disability progression, Kaplan–Meier curves will be constructed. A Long-rank and Cox proportional-hazards regression model will be used to analyze this endpoint. The fixed factors in the model will include treatment and relevant prespecified covariates . Additional baseline characteristics will be considered for inclusion in secondary models.

If the usual normality assumptions are not met, the endpoints will then be analyzed by either Poisson regression, using a model similar to the one to be used for the ARR, Wilcoxon Rank-Sum tests, or proportional odds logistic regression models, depending on the nature of the endpoints and whether covariates will be included in the model.

Safety

All treatment emergent signs and symptoms (those that initially occur after taking the first dose of study medication, or those that worsen after taking the first dose of study medication) will be summarized and tabulated according to their severity (mild, moderate, or severe) and relationship (definitely not related, or related) to study medication. The rates will be compared between each group and placebo using Fisher's Exact test.

Missing Data

Missing data of the lost to follow patients will be imputed by use of the last-observation-carried-forward (LOCF) approach.

We thank every and each one of you, for your total cooperation.

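### The empirical (sandwich) standard errors named for the primary relapse-rate test do not assure the stated 5% level if the analysed arms turn out small, and the protocol sets no floor on their size

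*Protocol*

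**What the plan says.** In Brief Statistical Methods, Primary Endpoint, the protocol fixes the model family and the source of the standard errors: "A Poisson regression/ negative Binomial analysis will be used to analyze this endpoint", with overdispersion handled by "basing standard errors on the empirical estimator of the parameter covariance matrix". Covariates enter too: "The fixed factors in the model will include treatment and relevant pre-specified covariates". Their number is not given. The level is set for every test: "Each test will be performed with a significance level of 0.05 (P-values will be two-tailed". Nothing is said about a finite-sample correction or about whether p-values come from z, t, chi-squared or F.

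On size, the summary at the front reads "Enrollment: Total number of MS patients in Cyprus meeting the required criteria", and Sample Size Estimation adds "Sample size will strictly be based on this subjects' availability parameter". No number and no minimum is given. Randomization and Masking divides whatever is recruited: "Patients will be randomly assigned to the four intervention groups". Missing Data Handling then narrows the set that matters most: "The overall key analysis should be based on per-protocol (excluding all protocol violations) supported by the ITT analyses".

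**The concern.** The empirical estimator is justified when there are many independent patients per arm. With few, it is biased downwards, because fitted residuals are smaller than true errors. A z or chi-squared reference then also ignores the noise in the variance estimate itself. Both faults act in the same direction: too many rejections and confidence intervals for the rate ratios that are too narrow. Adding covariates makes it worse.

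The design leaves room for this. Recruitment is from one country with no floor and four arms. The key analysis drops protocol violators after 30 months of daily intake, and the Note after the exclusion criteria counts a switch to an immunosuppressant, monoclonal antibody or other treatment as a drop-out. The protocol names exact tests for categorical baseline variables and for safety rates, but gives the primary efficacy test no comparable protection.

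What is at stake is the size of each single ARR test. This is separate from the multiplicity of three active arms and two endpoints.

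**Working it through.** **Stated figure.** The only figure to compare against is the nominal two-sided 0.05. The protocol states no sample size, power, relapse rate or dispersion.

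**Inputs from the protocol.** Four arms, 24 months on treatment (2.0 years), Poisson or negative binomial model, empirical covariance estimator, covariates of unstated number.

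**Inputs assumed.** Equal arms of 10 to 50 analysed patients, full follow-up, ARR 0.4 or 0.8, gamma-Poisson dispersion 0.5, 1 or 2, and 0 or 3 covariates.

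**Hand check of the mechanism.** With equal follow-up and no covariates, the sandwich variance of an arm's log rate is

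V = Σ(y − ȳ)² / (n·ȳ)²,

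that is, the sample variance with divisor n instead of n − 1. It is too small by the factor (n − 1)/n. Comparing the resulting statistic with 1.96 is like comparing a properly scaled one with 1.96·√((n − 1)/n). Treating that statistic as roughly t with 2n − 2 degrees of freedom gives:

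- n = 10: 1.96 × √0.90 = 1.86; on 18 df the two-sided tail is 7.9%.
- n = 20: 1.96 × √0.95 = 1.91; on 38 df, 6.4%.
- n = 50: 1.96 × √0.98 = 1.94; on 98 df, 5.5%.

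This approximation leaves out the skewness of relapse counts and the leverage of covariates, so it should sit near the lower end of a simulation. In this simple case the negative binomial model with sandwich standard errors gives the same test as Poisson, so the unresolved choice between the two does not matter here.

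**Simulation under no treatment effect.** Counts were gamma-Poisson with equal means in the four arms. A Poisson model was fitted with 4,000 trials per setting (2,000 at 50 per arm). Trials with an event-free arm were dropped (at most 3.2% at 10 per arm). The plain version uses the unmodified sandwich with z or 3-df chi-squared. The corrected version uses an HC3-type sandwich with t or F on residual degrees of freedom. Entries are rejection rates in %, as the range over relapse rate, dispersion and covariates.

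| Analysed per arm | One arm vs placebo, plain | 3-df test, plain | One arm vs placebo, corrected | 3-df test, corrected |
|---|---|---|---|---|
| 10 | 7.9-12.9 | 9.6-21.2 | 2.8-7.1 | 1.8-8.4 |
| 15 | 6.6-10.6 | 7.7-16.4 | 4.1-7.0 | 3.7-9.0 |
| 20 | 6.0-9.3 | 7.2-14.0 | 4.4-6.5 | 4.3-7.6 |
| 30 | 5.9-8.2 | 6.9-10.8 | 4.7-6.3 | 4.5-7.5 |
| 50 | 5.1-6.7 | 5.1-8.4 | 4.2-5.9 | 4.2-6.2 |

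For a single test at 5%, the Monte Carlo standard error is √(0.05 × 0.95/4,000) = 0.34 percentage points, or 0.49 with 2,000 trials. Differences of a few tenths carry no meaning.

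Separate runs with four covariates (ARR 0.5-0.8, dispersion 0.5-1) gave, for the plain 3-df test, 16-20% at 10 per arm and 10-13% at 20. For one arm versus placebo they gave 10-13% and 7-9%. These agree with the table to rounding.

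**The case against.** The strongest objection is that the defect is partly read into the text. The protocol does not call the estimator uncorrected and does not prescribe large-sample p-values. HC3 and Mancl-DeRouen estimators are themselves empirical estimators, so a correction could be added without contradicting the sentence, and it may stand in an analysis plan that is not at hand. This holds as a limit on the claim: what is criticised is the ordinary reading of an unqualified statement. It does not remove the point. The protocol does choose an estimator and a level, and leaves open the one quantity, patients per arm, that decides whether the two are compatible.

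Second, nothing in the protocol says that the trial will be small. It aims at every eligible patient in the country, and Sample Size Estimation expects that enough will probably enrol. That also stands: 10 or 20 per arm is an assumption.

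Third, the largest figures belong to a 3-df test that the protocol never names. Missing Data Handling frames the question against placebo, while Brief Statistical Methods defines success only as a significant difference between treatments. Both tests are therefore reported, and the contrast with placebo shows the smaller excess.

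A reader might infer from the table that this trial rejects a true null 1.5 to 4 times too often. The documents do not support that as a property of the trial. A factor near 4 (21.2/5 = 4.2) needs about 10 or fewer analysed patients per arm, high dispersion, covariates and the 3-df test. At 20 per arm, one arm versus placebo runs at 6.0/5 = 1.2 to 9.3/5 = 1.9 times nominal.

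**Conclusion.** The point holds in conditional form. With the sample size open and the analysis narrowed to the per-protocol set, the named standard errors, read as an unmodified sandwich with z or chi-squared p-values, do not guarantee the stated 5%. Below about 30 analysed patients per arm the excess is material: at 20 per arm about 6-9% for one arm versus placebo and 7-14% for a 3-df test, and at 10 per arm about 8-13% and 10-21%. At 50 or more it is slight (about 5-7% and 5-8%). All these figures rest on assumed arm size, relapse rate, dispersion and number of covariates, with equal arms and full follow-up. The documents do not show that the arms will be small or that a correction has been ruled out. The change is worth making because the method should hold its level at whatever size recruitment yields.

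**What to change.** In Brief Statistical Methods, Primary Endpoint, state that standard errors will come from a leverage-corrected empirical estimator (HC3 or Mancl-DeRouen type), and that tests and confidence intervals will use t or F reference distributions on residual degrees of freedom. This should be fixed before unblinding.

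A re-randomisation test of the same treatment contrast, run under the allocation scheme actually used, may be added as a sensitivity check in the ITT set only. In the per-protocol set it is not assured to be exact, because membership may depend on treatment. The scheme would have to be documented, since the protocol says little more than that it is central.

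The cost is a sentence and a standard software option, with no change to patients or procedures. Intervals become somewhat wider, and the test is somewhat conservative at about 10 per arm with covariates. The correction is not exact: over the range examined the level runs from about 2% to 8% at 10 per arm and 4% to 8% at 20, with the upper values where dispersion is high. If the arms prove large, it changes almost nothing.

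### A normality-based fallback is attached to time to confirmed disability progression, whose log-rank/Cox analysis assumes no normality; read literally, it replaces that analysis without fixing one test

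*Protocol*

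**What the plan says.** All of this is in the protocol, in Brief Statistical Methods unless another section is named.

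- Key secondary endpoint, planned analysis: "A Long-rank and Cox proportional-hazards regression model will be used to analyze this endpoint". Kaplan–Meier curves accompany it. The model holds treatment and pre-specified covariates, and then: "Additional baseline characteristics will be considered for inclusion in secondary models".
- Next paragraph, same heading: "If the usual normality assumptions are not met, the endpoints will then be analyzed by either Poisson regression", the Poisson model being like the one for the annualized relapse rate (ARR). The other options are "Wilcoxon Rank-Sum tests, or proportional odds logistic regression models, depending on the nature of the endpoints and whether covariates will be included in the model".
- Primary endpoint (ARR): "A Poisson regression/ negative Binomial analysis will be used to analyze this endpoint", with empirical standard errors.
- Success rule: "The study will be considered successful if there is a significant difference between the treatments for either of the two endpoints". Each test is two-sided at 0.05.

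No normality check, threshold or timing is given, and no order among the three alternatives.

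**The concern.** A fallback should be triggered by failure of an assumption that the planned analysis makes. Here the planned analysis is log-rank and Cox, and neither assumes a normal distribution. The condition is therefore either empty (there is no such assumption to fail) or, if applied to the observed times, always satisfied. On the second reading the sentence directs a replacement, not a sensitivity analysis, and the planned survival analysis never stands.

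Two of the three replacements, rank-sum and proportional odds, do not account for censoring. The sections Drop Outs and Missing Data Handling foresee drop-outs and patients lost to follow-up, so censoring before month 24 is to be expected. Because significance on this endpoint alone counts as success, an unfixed test here bears directly on the trial's claim.

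**Working it through.** **Step 1. Does any planned efficacy analysis rest on normality?**

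| Endpoint | Planned analysis | Normality assumed? |
|---|---|---|
| ARR | Poisson / negative binomial, empirical standard errors | No |
| Time to confirmed progression | Kaplan–Meier, log-rank, Cox | No |

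The sentence has no efficacy analysis to which it properly applies.

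**Step 2. Would the trigger be met if applied to the observed times?** Event-free completers all share the value 24 months. In simulated trials with progression read at months 3, 9, 15, 21 and 24, a Shapiro–Wilk test rejected normality in 100% of runs in all six scenarios (4,000 runs each).

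**Step 3. Inputs for the size of the problem.** The protocol states no sample size, event rate or dropout rate, so there is no figure of its own to reproduce. Assumed: one active arm against placebo, 20 or 40 per arm, no treatment effect, 0.2 progression events per year. Over two years that is 1 − exp(−0.2 × 2) = 1 − exp(−0.4) = 0.33 progressing. The visit-based runs used 20% or 35% by month 24. With 4,000 runs, the Monte Carlo standard error at 5% is √(0.05 × 0.95 / 4000) = 0.0034.

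**Step 4. False-positive rate when the smallest p-value is taken, equal 20% dropout.**

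| Candidate set | 20 per arm | 40 per arm |
|---|---|---|
| Log-rank alone | 5.1% | 5.0% |
| Log-rank plus the three substitutes | 8.8% | 8.3% |
| The three substitutes only | 8.5% | 8.2% |
| Rank-sum with event-free drop-outs carried to month 24, Poisson, and a proportion test | 6.9% | 6.4% |

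In rows two and three, a rank test on ordered event time stands in for proportional odds. The proportion test in the last row is not named in the protocol. The visit-based runs gave 8.2–8.9% for log-rank plus three substitutes with equal dropout (10%, 20% or 30%). Log-rank alone stayed at 4.4–5.4% in every visit-based scenario, including unequal dropout. The range for a free choice is thus about 6–9%.

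**Step 5. Single substitutes under unequal dropout (10% against 40%, no effect).**

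| Test | 20 per arm | 40 per arm |
|---|---|---|
| Log-rank | 5.4% | 5.3% |
| Rank-sum on raw follow-up time | 22–23% | 39–45% |
| Rank-sum, event-free drop-outs carried to month 24 | 6.6% | 7.4% |

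The spread in the middle row comes from separate sets of runs at the same nominal dropout, so the figure is sensitive to simulation settings that the protocol does not fix. At 10% against 20% dropout, the raw-time rank-sum gave 6.6% and 9.1%. Raw time inflates because leaving at month 9 is scored like progressing at month 9. Poisson with person-time did not exceed 5% in any of these runs (1.5–4.1% in the visit-based set).

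**The case against.** The strongest defence is that the sentence is generic wording that strayed under this heading. It speaks of endpoints in the plural and of differing nature, and the protocol does collect continuous measures (blood counts, biochemistry and membrane lipids, under Blood Sample). If log-rank and Cox have no normality assumption, nothing can fail and the planned analysis stands. This is plausible, but the laboratory measures are not called endpoints and the sentence sits under time to progression. A reader cannot tell which reading is meant.

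Several stronger inferences should be resisted:

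- *The analyst may pick freely after seeing results.* The text ties the choice to endpoint type, known in advance, and to covariate use. Main-model covariates are pre-specified; additional ones are open only for secondary models. Under Randomization and Masking, statisticians are unaware of assignments throughout the study. These limits are real, but they still do not name one test.
- *All the substitutes are invalid.* Poisson with a person-time offset handles censoring and held its level.
- *The ARR analysis is displaced too.* The sentence uses the ARR model as its point of reference, so it does not target ARR.
- *False positives of 20–45% are to be expected.* That needs a rank-sum test on raw follow-up time, a variable the protocol never names, together with strongly unequal dropout. The protocol asks for drop-outs to be followed like other participants, specifies last observation carried forward for patients lost to follow-up, and matches the products in appearance and smell.

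A statistical analysis plan, not at hand, could settle which test applies. It would have to override the protocol's stated trigger, not merely fill in a detail.

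**Conclusion.** The point stands as a wrongly stated rule. The trigger does not belong to the planned analysis; read literally, it replaces log-rank and Cox on an endpoint that can by itself declare success; and the text does not fix which of three methods takes over. The size is modest on reasonable assumptions: about 6–9% false positives instead of 5% for one comparison if the most favourable candidate is taken. That is an upper bound on the harm from choice, since blinding and the partial rule restrain it. It rests on assumed arm sizes, event rate and dropout. Larger inflation is possible for rank-sum on raw follow-up time, but it depends on the dropout imbalance and on how lost patients' times are set, so it should not be quoted as the expected effect. Which count model to use for ARR is a separate matter and forms no part of this point.

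**What to change.** Delete the normality sentence for this endpoint, or limit it explicitly to continuous outcomes such as laboratory values. In its place state, for example:

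*Time to confirmed disability progression is tested by the log-rank test, with a Cox model for the hazard ratio, irrespective of the distribution of the observed times. Any alternative model is a sensitivity analysis and does not replace the log-rank p-value.*

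This changes wording only. It adds no patients, visits or data, and no sample-size figure changes because none is stated. The one thing given up is the freedom to report another test as the main result for this endpoint.

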At The Cyprus Institute of Neurology And Genetics By PALUPA Medical Ltd. (Incubation Company)

Any and all information presented in this document shall be treated as confidential and shall remain the exclusive property of PALUPA Medical Ltd. The use of such confidential information must be restricted to the recipient for the agreed purpose and must not be disclosed, published or otherwise communicated to any unauthorized persons, for any reason, in any form whatsoever without the prior written consent of PALUPA Medical Ltd.

Project Title:

Proof-of-Concept Clinical Trial:

Novel medical nutrition formulas as possible new approach for relapsing multiple sclerosis treatment: a double-blind, randomized, placebo-controlled proof-of-concept clinical trial.

Clinical Trial Protocol and Project Design

Completed

Version Number: electronic version FINAL

Date: 1st June 2005 Total number of pages: 16

PALUPA Medical Ltd.

Project Funded By: Cyprus Ministry of Commerce, Industry and Tourism, program for the creation of new high technology and innovation enterprises through the business incubator.

PROTOCOL

Medical Nutrition Formulas for the Treatment of Relapsing Multiple Sclerosis

A Single-Center, Parallel-group, Proof-of-Concept, Double-blind, Randomized, Placebo-Controlled, Trial of Efficacy and Safety.

Purpose

The purpose of this proof-of-concept study is to determine the safety and efficacy of three novel

interventions in the treatment of individuals who have been diagnosed with relapsing remitting

multiple sclerosis (MS). We intend to evaluate the therapeutic ability of PLP10 and of two other

interventions consisting of PLP10 constituent partial fractions versus placebo, when used in

patients with relapsing remitting (RR) MS. It is hoped that the agents used for the composition of

the interventions in general will be able to normalize structural molecules of cell membranes,

normalize phospholipase function and immune system, normalize endoplasmic reticulum

function/stress, specific gene expression, quench free nitro- and oxo- free radical derivatives,

elevate anti-inflammatory cytokines, halt apoptosis, normalize metalloproteinases function,

supply major building blocks for myelin formation/reformation, promote remyelination and

neuroprotection and so halt inflammation and all related cascade of events leading to the MS

pathogenesis. All these simultaneously involved pathogenic mechanisms as a result of multiple

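### The protocol asks how safe the formulas are against placebo, but the only between-group safety comparison it states is a significance test, which does not show how large an excess of harm the data still allow

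*Protocol*

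**What the plan says.** Safety is a named aim. The Purpose section opens with "The purpose of this proof-of-concept study is to determine the safety and efficacy of three novel" interventions, and Missing Data Handling states the main question as relapse reduction first and "secondly the disability accumulation when used in RRMS patients and how safe it is vs. placebo".

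Under Brief Statistical Methods, the Safety paragraph says that treatment-emergent signs and symptoms "will be summarized and tabulated according to their severity (mild, moderate, or severe) and relationship" to study medication. It then fixes the comparison: "The rates will be compared between each group and placebo using Fisher's Exact test". The general rule earlier in that section applies to it: "Each test will be performed with a significance level of 0.05 (P-values will be two-tailed").

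On size, Randomization and Masking says "Patients will be randomly assigned to the four intervention groups". Sample Size Estimation leaves the number to patient availability and states: "Power calculations could not be done before the study because of the lack of information from previous studies on potential effect sizes". The protocol gives no patient number, allocation ratio or expected adverse event rate.

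**The concern.** How safe a formula is relative to placebo is a question about the size of a difference. The comparison that the protocol fixes for it is a test of whether the difference is zero. A significant result would signal harm. A non-significant one would leave the reader without a stated measure of the excess harm that is still compatible with the data.

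The gap is clearest beside the efficacy plan. For the annualized relapse rate the same section commits to reporting a relative reduction as well as a model-based test. For safety it commits to group tabulations and a p-value.

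The safety half of the main question is at stake. With arms formed by a four-way split of whoever is available, and no power calculation, a non-significant result for an uncommon event could easily reflect small numbers.

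**Working it through.** **Inputs from the protocol.** Fisher's exact test of each active group against placebo; two-sided 0.05; four arms. There is no stated safety power or event rate, so there is no figure of the plan's own to reproduce.

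**Assumptions.** Equal arms of n patients; each patient counted once per event; placebo rates p from 2% to 20%; active rate 3p.

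**Step 1: power of the stated test.** Power = Σ over (i, j) of Bin(i; n, p) × Bin(j; n, 3p), summed over outcomes with j > i and Fisher two-sided p ≤ 0.05. Exact enumeration gives:

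| Placebo → active | n = 10 | 20 | 30 | 40 | 50 | 70 | 100 |
|---|---|---|---|---|---|---|---|
| 5% → 15% | 0.006 | 0.070 | 0.093 | 0.183 | 0.244 | 0.407 | 0.586 |
| 10% → 30% | 0.057 | 0.242 | 0.372 | 0.534 | 0.640 | 0.813 | 0.935 |
| 15% → 45% | 0.141 | 0.443 | 0.645 | 0.793 | 0.887 | 0.969 | 0.996 |
| 20% → 60% | 0.253 | 0.650 | 0.851 | 0.947 | 0.982 | 0.998 | 1.000 |

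For 2% → 6%, power is 0.032 at 50 per arm and 0.171 at 100.

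**Step 2: where a miss becomes less likely than detection.**
- For 10% → 30%, power is 0.488 at n = 37 and 0.504 at n = 38. The continuity-corrected normal approximation gives 41. Hence about 40 per arm.
- For 5% → 15%, power is 0.481 at n = 80 and 0.508 at n = 84. The approximation gives 89. Hence about 80 to 90 per arm.
- For 20% → 60%, the approximation gives 17, and exact power at n = 20 is already 0.650.

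**Step 3: rare events.** With 0 events on placebo and k on active in equal arms, the two-sided Fisher p-value is 2 × C(n, k) / C(2n, k).
- k = 4, n = 10: 2 × 210 / 4845 = 0.087.
- k = 4, n = 20: 2 × 4845 / 91390 = 0.106.
- k = 4, n = 30, 40, 50 and 70: 0.112, 0.116, 0.117 and 0.120.
- k = 5 is significant at n = 10 (0.033) and n = 20 (0.047), but not at n = 30 (0.052) or at 40, 50 and 70.
- k = 6 is significant at all six sizes.

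So four serious adverse events on one formula and none on placebo would be non-significant at every one of these arm sizes.

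**Step 4: what an interval would add.** These are illustrative counts with Newcombe 95% intervals for the risk difference:

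| Per arm | Placebo vs active | Fisher p | Difference (95% CI), percentage points |
|---|---|---|---|
| 20 | 1 vs 3 | 0.60 | +10 (−11 to +31) |
| 20 | 2 vs 6 | 0.24 | +20 (−5 to +43) |
| 30 | 3 vs 9 | 0.10 | +20 (−1 to +39) |
| 50 | 2 vs 6 | 0.27 | +8 (−3 to +20) |

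All four are non-significant, and in each the data still allow an excess of 20 points or more. With no events in an arm, the two-sided 95% upper limit for its true rate is 1 − 0.025^(1/n): 16.8% at n = 20, 11.6% at n = 30 and 7.1% at n = 50.

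**The case against.** The strongest objection is that intervals for adverse event tables, and the wording of results, usually belong in a statistical analysis plan, which may exist here but is not shown. Fisher's test is conventional for small counts, and nothing in the protocol forbids adding intervals. This has weight: the missing interval alone would not be a finding. But the protocol did not leave the safety comparison open. It fixed one, and the one it fixed does not match the question it asks.

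Three stronger readings are tempting, and the document supports none of them.

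- *A tripled event rate would usually go undetected.* Step 1 shows that this reverses for common events and larger arms, and the protocol gives neither rates nor arm size.
- *Safety rests on Fisher's test alone.* The protocol also plans tables by severity and relationship, haematology and biochemistry, a safety monitoring committee and a data monitoring committee. A reader could compute differences from tables that give counts by group. Fisher's test is only the sole between-group comparison stated.
- *The sponsor will read non-significance as safety.* No section says so, and the success rule in Brief Statistical Methods follows the two efficacy endpoints. The protocol merely leaves that misreading open.

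It is also fair to say that low power for uncommon events is general in small proof-of-concept trials. Intervals would show the imprecision, not remove it.

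**Conclusion.** The point holds in a limited form. The stated comparison tests for a difference in adverse event rates but does not measure it, while the protocol asks "when used in RRMS patients and how safe it is vs. placebo". The consequence is material for uncommon events in small arms. A tripling is more likely missed than found below about 40 per arm at a 10% placebo rate, and below about 80 to 90 per arm at 5%. For very rare events, 0 against 4 does not reach significance at any size checked from 10 to 70. For events at 20% or more on placebo the test usually detects a tripling from about 20 per arm.

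These figures rest on assumed equal arms and assumed event rates. They do not show that this trial would miss a given harm. No efficacy result or success criterion is affected. This is a cheap improvement that would change what the trial can say about harm.

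**What to change.** In Brief Statistical Methods, Safety, add wording to this effect: *For treatment-emergent adverse events and for serious adverse events, the proportion of patients affected in each group and the difference of each active group from placebo will be reported with a 95% confidence interval (for example Newcombe or exact). Fisher's exact p-values will be given as descriptive flags. A non-significant p-value will not be taken as evidence of safety.*

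No acceptance rule on the upper confidence limit is proposed, because the protocol defines no margin for excess harm.

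The cost is two or three sentences and a few table columns, with no new data and no change of design. The downside is that wide intervals will make the safety statement look less favourable.
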